10.4.3 Missing Data

The primary analysis will be completed on the FAS with available data per subject, assuming the overall study discontinuation rate is $<5\%$. If the overall study discontinuation rate is $\geq 5\%$ then the primary analysis will be based on the primary imputation methodology as defined [Section 10.4.5](#) and the available data analyses will become robustness analyses.

Additionally, robustness analyses will include repeating the primary analysis on the per protocol set (PPS); the FAS imputing missing data using last observation carried forward (LOCF); the FAS imputing missing data using Markov Chain Monte Carlo (MCMC) multiple imputation methodology under different assumptions of missingness (at random and not at random) each using 30 imputed values.

The imputation model, for each visit, under the assumption of missing **at random** is:

```
PROC MI DATA=INDATA SEED=50048 OUT=OUTDATA1 MINIMUM = 0 MAXIMUM = 3 ROUND  
= 1 NIMPUTE=30;  
  MCMC INITIAL=EM;  
  BY <TREATMENT>;
```

```
VAR <BASELINE> <PARAMETER>;
RUN;
where PARAMETER has 5 levels and refers to the corneal fluorescein staining
score for each region (inferior, superior, central, temporal, and nasal).
The imputation model, for each visit, under the assumption of missing not at
random is:
PROC MI DATA=INDATA SEED=35852 OUT=MDATA MINIMUM = 0 MAXIMUM = 3 ROUND =
1 NIMPUTE=30;
  MCMC IMPUTE=MONOTONE;
  VAR <BASELINE> <PARAMETER>;
RUN;

PROC MI DATA=MDATA SEED=48778 OUT=OUTDATA2 MINIMUM = . 0 0
  MAXIMUM = . 3 3 ROUND = . 1 1;
  CLASS <TREATMENT>;
  MONOTONE REG(<PARAMETER> = <BASELINE> / DETAILS);
  MNAR MODEL(<PARAMETER> / MODELOBS=(<TREATMENT>='Saline'));
  VAR <TREATMENT> <BASELINE> <PARAMETER>;
RUN;
```

where PARAMETER has 5 levels and refers to the corneal fluorescein staining score for each region (inferior, superior, central, temporal, and nasal).

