6.5.7 Analysis of Efficacy

6.5.7.1 Descriptive Statistics

Quantitative variables will be summarized using number of subjects (n), mean, median, standard deviation, minimum and maximum. The mean, median, and standard deviation will be presented with one more decimal place than the collected data and the minimum and maximum will be presented with the same decimal places as the collected data. The qualitative variables will be summarized using counts and percentages. Summaries will be presented by treatment group in the FAS and PPS.

All primary and secondary analyses will be two-sided at a significance level of 0.05.

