Least squares mean for each treatment group and for the difference between treatment groups will be presented from each model together with two-sided p-values (used for primary inference) and 95% confidence intervals.

Sample SAS ANCOVA code:

```
PROC GLM DATA=INDATA;
  CLASS <TREATMENT>;
  MODEL <ENDPOINT>=<TREATMENT> <BASELINE>;
  LSMEANS <TREATMENT> / CL ALPHA=0.05;
  LSMEANS <TREATMENT> / PDIFF CL ALPHA=0.05;
RUN;
```

Additional robustness analyses will include repeating the primary analysis on the PPS; the FAS imputing missing data using last observation carried forward (LOCF); the FAS imputing missing data using MCMC multiple imputation methodology under different assumptions of missingness (at random and not at random) each using 30 imputed values.

Sample SAS MCMC MI (missing at random):

```
PROC MI DATA=INDATA SEED=97656 OUT=OUTDATA MINIMUM=0 MAXIMUM=3 ROUND=1
NIMPUTE=30;
  MCMC INITIAL=EM;
  BY <TREATMENT>;
  VAR <BASELINE> <PARAMETER>;
RUN;
```

Where <PARAMETER> has 5 levels and refers to the CFS for each region (inferior, superior, central, temporal, and nasal).

Sample SAS MCMC MI (not missing at random):

```
PROC MI DATA=INDATA SEED=36797 OUT=MDATA MINIMUM=0 MAXIMUM=3 ROUND=1
NIMPUTE=30;
```

```
  MCMC IMPUTE=MONOTONE;
  VAR <BASELINE> <PARAMETER>;
RUN;
```

```
PROC MI DATA=MDATA SEED=38549 OUT=OUTDATA2 MINIMUM=. 0 0 MAXIMUM=. 3 3
ROUND=. 1 1;
  CLASS <TREATMENT>;
  MONOTONE REG(<PARAMETER>=<BASELINE> / DETAILS);
  MNAR MODEL(<PARAMETER> / MODELOBs=(<TREATMENT>='Saline'));
  VAR <TREATMENT> <BASELINE> <PARAMETER>;
RUN;
```

Where <PARAMETER> has 5 levels and refers to the CFS for each region (inferior, superior, central, temporal, and nasal).

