6.5.10 Determination of Sample Size

The statistical hypotheses for the primary endpoint of CFB corneal fluorescein staining (NEI scale) total score at Day 57 are as follows:

H_{01} : The difference, between study eyes treated with NOV03 and study eyes treated with saline, in the mean CFB corneal fluorescein staining (NEI scale) total score at Day 57 = 0.

H_{A1} : The difference, between study eyes treated with NOV03 and study eyes treated with saline, in the mean CFB corneal fluorescein staining (NEI scale) total score at Day 57 \neq 0, with superiority claimed if the difference is less than 0 (NOV03 minus saline).

The statistical hypotheses for the hierarchical primary endpoint of the CFB Dryness Score at Day 57 are as follows:

H_{02} : The difference, between subjects treated with NOV03 and subjects treated with saline, in the mean CFB Dryness Score at Day 57 = 0.

H_{A2} : The difference, between subjects treated with NOV03 and subjects treated with saline, in the mean CFB Dryness Score at Day 57 $\neq 0$, with superiority claimed if the difference is less than 0 (NOV03 minus saline).

Two hundred fifty (250) subjects (study eyes) per treatment group yields 97.9% power to reject H_{01} in favor of H_{A1} and conclude superiority of NOV03 over saline in the mean CFB tCFS score at Day 57 assuming a true difference (NOV03 minus saline) of -1.0, a common standard deviation of 2.8, and a two-sided alpha = 0.05. Two hundred fifty (250) subjects per treatment group yields 97.9% power to reject H_{02} in favor of H_{A2} and conclude superiority of NOV03 over saline in the mean CFB Dryness Score (VAS) at Day 57 assuming a true difference (NOV03 minus saline) of -10, a common standard deviation of 28, and a two-sided alpha = 0.05. Accounting for an assumed 10% subject discontinuation rate, approximately 560 subjects (280 subject each arm) will be randomly assigned to trial treatment such that approximately 250 evaluable participants per arm complete the trial.

Therefore, assuming independence between tCFS score and Dryness Score (VAS), 250 FAS subjects per treatment group at Day 57 yields $97.9\% * 97.9\% = 95.8\%$ power to reject both H_{01} and H_{02} . A positive correlation between these two endpoints would increase the overall power.

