7 INDEX OF PLANNED TABLES, FIGURES, AND LISTINGS

Tables

Number	Title
14.1.1.1	Overall Disposition and Subject Accountability – FAS
14.1.1.2	Overall Disposition and Subject Accountability – PPS
14.1.1.3	Overall Disposition and Subject Accountability – SAF
14.1.2.1	Overview of Analysis Sets – Randomized Subjects
14.1.2.2	Reasons for Exclusion from Study Populations – Randomized Subjects
14.1.3	Major Protocol Deviations – FAS
14.1.4.1	Demographic and Baseline Characteristics – FAS
14.1.4.2	Demographic and Baseline Characteristics – PPS
14.1.4.3	Demographic and Baseline Characteristics – SAF
14.1.5.1	Baseline Ocular Characteristics – FAS
14.1.5.2	Baseline Ocular Characteristics – PPS
14.1.5.3	Baseline Ocular Characteristics – SAF
14.1.6.1	Study Eye Ocular Medical History – FAS
14.1.6.2	Fellow Eye Ocular Medical History – FAS
14.1.6.3	Subject Level Ocular Medical History – FAS
14.1.6.4	Non-ocular Medical History – FAS

- 14.1.7.1 Study Eye Ocular Concomitant Medications – FAS
- 14.1.7.2 Fellow Eye Ocular Concomitant Medications – FAS
- 14.1.7.3 Subject Level Ocular Concomitant Medications – FAS
- 14.1.7.4 Non-ocular Concomitant Medications – FAS
- 14.1.8 Study Medication Exposure and Compliance – SAF
- 14.2.1.1 Analyses of Change from Baseline tCFS and Dryness Score (VAS) at Day 57 – FAS
- 14.2.1.2 Analyses of Change from Baseline tCFS and Dryness Score (VAS) at Day 57 – PPS
- 14.2.2 Robustness Analyses of Change from Baseline tCFS and Dryness Score (VAS) at Day 57 (Discontinuation Rate $\geq 5\%$) – FAS
- 14.2.3 Sensitivity Analyses of Change from Baseline tCFS and Dryness Score (VAS) at Day 57 – FAS
- 14.2.4.1 Analyses of Secondary Efficacy Endpoints – FAS
- 14.2.4.2 Sensitivity Analyses of Secondary Efficacy Endpoints – FAS
- 14.2.5.1 Analysis of Dryness Score (VAS) – FAS
- 14.2.5.2 Sensitivity Analysis of Dryness Score (VAS) – FAS
- 14.2.6.1 Analysis of Study Eye tCFS – FAS
- 14.2.6.2 Analysis of Fellow Eye tCFS – FAS
- 14.2.6.3 Sensitivity Analysis of Study Eye tCFS – FAS
- 14.2.6.4 Sensitivity Analysis of Fellow Eye tCFS – FAS
- 14.2.7.1 Analysis of Study Eye Central Sub-region CFS (NEI scale) – FAS
- 14.2.7.2 Analysis of Fellow Eye Central Sub-region CFS (NEI scale) – FAS
- 14.2.7.3 Sensitivity Analysis of Study Eye Central Sub-region CFS (NEI scale) – FAS
- 14.2.7.4 Sensitivity Analysis of Fellow Eye Central Sub-region CFS (NEI scale) – FAS
- 14.2.7.5 Analysis of Study Eye Inferior Sub-region CFS (NEI scale) – FAS

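### The second step of the not-at-random tCFS imputation reads 30 stacked copies of the trial as one data set, so the standard error of that check can come out about 5.5 times too small

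*SAP*

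**What the plan says.** SAP 6.5.7.3 gives sample SAS code for a not-at-random multiple imputation of corneal staining, as one of the robustness analyses of the primary comparison.

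- **Step 1** fills the data to a monotone pattern and, with `NIMPUTE=30` on its next line, writes the result to MDATA: "PROC MI DATA=INDATA SEED=36797 OUT=MDATA MINIMUM=0 MAXIMUM=3 ROUND=1".
- **Step 2** imputes the remaining missing grades from a regression fitted to saline records: "PROC MI DATA=MDATA SEED=38549 OUT=OUTDATA2 MINIMUM=. 0 0 MAXIMUM=. 3 3". Its only further statements are CLASS, MONOTONE REG, MNAR and VAR.
- **Scope.** The code is for the regional grades: "Where <PARAMETER> has 5 levels and refers to the CFS for each region".

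Protocol 10.4.3 prints the same two steps with different seeds, the second being "PROC MI DATA=MDATA SEED=48778 OUT=OUTDATA2 MINIMUM = . 0 0". The accompanying text in Protocol 10.4.3, repeated in SAP 6.5.7.3 and 6.5.8.6.1, promises at-random and not-at-random imputation, "each using 30 imputed values".

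SAP section 7 lists the output as Table 14.2.2, "Robustness Analyses of Change from Baseline tCFS and Dryness Score (VAS) at Day 57". The rest of that title restricts the table to a discontinuation rate of 5% or more.

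**The concern.** Step 2 has nothing that tells the procedure MDATA is 30 imputations and not one data set. The saline regression is then fitted to 30 rows per subject, and every second-step imputation carries 30 rows per subject. The number of second-step draws is left to the software, so the code does not deliver the 30 imputations in the text.

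This is unlikely to be shorthand. The at-random block printed just above it in the SAP writes out both `NIMPUTE=30` and a BY statement.

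No later code repairs it. Neither document shows the regional grades being summed to tCFS, an ANCOVA by imputation, or pooling, and the one ANCOVA block in the SAP has no BY statement.

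What is at stake is the credibility of a robustness check. This is the only planned analysis that imputes missing NOV03 outcomes from the saline arm. The plan assumes 10% discontinuation, above its own 5% trigger, so Table 14.2.2 is an expected output. Such a check is read through its confidence interval and p-value, which are exactly what the stacking distorts.

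**Working it through.** **Inputs**

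- tCFS planning values and test level (SAP 6.5.10): "assuming a true difference (NOV03 minus saline) of -1.0, a common standard deviation of 2.8, and a two-sided alpha = 0.05"; 250 evaluable and 280 randomised per arm, 10% discontinuation.
- 30 imputations written by step 1 (SAP 6.5.7.3).
- Five regions graded 0 to 3, total 0 to 15 (SAP 6.5.4.1.7).
- Assumption: 5 or 25 second-step draws, because the documents give no number.

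**1. The plan's own figure.** SE = 2.8 × √(2/250) = 0.2504. Then 1.0/0.2504 = 3.993, and Φ(3.993 − 1.960) = Φ(2.033) = 0.979. This reproduces the stated 97.9%, so the planning inputs are sound.

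**2. What MDATA contains.** Step 2 gives three bounds, for treatment, one baseline and one parameter, so each region is handled singly. With baseline observed, baseline plus one outcome is already a monotone pattern. Step 1 then has nothing to fill, and MDATA is 30 identical copies: 30 × 560 = 16,800 rows, or 8,400 per arm.

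**3. Standard error, with the ANCOVA run within each second-step imputation.**

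- Correct: 2.8 × √(2/280) = 0.2366.
- Stacked: 2.8 × √(2/8,400) = 0.0432.
- Ratio: √30 = 5.48.

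Rubin's rules do not restore the lost variance. The missing grades are drawn separately in each copy and the regression is fitted to 30 times the records, so the between-imputation variance shrinks as well.

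**4. False-positive rate of the check.** Nominal significance now needs only |z| > 1.96/5.477 = 0.358 on the correct scale. Under no effect that has probability 0.72 two-sided, 0.36 in each direction.

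**5. Simulation of the printed code.** Regional grades 0 to 3, saline-based regression with parameter draws, bounds and rounding, sum to tCFS, ANCOVA, Rubin pooling, 280 per arm, no true effect:

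| Missing | Trials | Second-step draws | SE ratio | Rejection, by imputation | Rejection, stacked | Stacked, favouring NOV03 |
|---|---|---|---|---|---|---|
| 10% | 1,200 | 25 | 5.49 (0.208 vs 0.038) | 3.7% | 72.3% | 39.0% |
| 10% | 1,000 | 5 | 5.47 | – | 69.4% | 36.3% |
| 5% | 600 | – | 5.49 | 5.0% | 73.0% | 36.5% |

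A dash means not recorded. Done by imputation, significance in favour of NOV03 was 1.9% in the first row and 3.0% in the third. Two smaller independent null runs at 10% missing gave 66% against 4.5% (200 trials) and 63% against 5% (60 trials). With a true effect the ratio was 5.48 to 5.53 at 5% to 15% missing, and the two point estimates agreed to within 0.003 (for example −0.806 and −0.805 in 400 trials). The absolute SEs are illustrative; the ratio is stable.

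**6. The other way to group the output.** If rows are grouped by the first-step index instead, each subject appears once per second-step draw. The factor is then √5 = 2.24 to √25 = 5, and null rejection is 38% to 70%.

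**7. What this does to the check.** At the simple SE, a significant primary result needs a difference of about 1.96 × 0.2366 = 0.46 points. The stacked check needs 1.96 × 0.0432 = 0.085 points, 18% of that. If saline-based imputation removes the effect in 10% of subjects, it shrinks the estimate by about 10% on average. The stacked check would therefore almost never disagree with a significant primary result.

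**The case against.** - **It is sample code, and the 5.5 depends on an unwritten step.** True. The SAP labels the block as sample code, and the text asks for 30 imputations, so a careful programmer may correct it silently. The protocol is firmer and presents its block as the imputation model. The other grouping gives 2.2 to 5 instead of 5.5 (assuming 5 to 25 draws), which is still materially wrong. Neither way of grouping the printed output gives a valid standard error.
- **The error might be noticed.** Also fair. If n is tabulated with the result, 8,400 per arm against 280 would stand out. That is a chance of detection, not a safeguard in the plan.
- **The 72% overstates the practical harm.** This has weight, because the check is read beside the primary result. The relevant event is a significant primary result for NOV03, a correct check that is not significant, and a stacked check that is. A separate simulation (continuous outcome, residual SD 2.8, 280 per arm, available-data ANCOVA as primary) put this at 1.1% of null trials with 10% missing and 0.5% with 5%. At the planned −1.0 it was 1.9% and 0.2%. At −0.5 with 10% missing it was 8.4%, and among null trials with a significant primary result it was 40% (10% missing) or 22% (5% missing). The harm therefore falls on borderline trials, which are the ones a robustness check exists for.
- **The Dryness Score.** Table 14.2.2 covers both primary endpoints, but the code covers only staining. The printed code does not touch the Dryness Score; its not-at-random imputation is simply not specified.

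**Conclusion.** The concern holds. Followed as printed, the second step treats 30 imputations as one data set in both the SAP and the protocol, and nothing elsewhere in either document corrects it.

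The standard error of the not-at-random tCFS analysis is too small by 5.48 if the ANCOVA is run within second-step imputations and pooled. It is too small by about 2.2 to 5 if the output is grouped by the first-step index, assuming 5 to 25 draws. The √30 figure rests on baseline being observed, so that step 1 yields identical copies.

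The reach is limited. The point estimate is not biased by the omission, and no success criterion uses this analysis. The primary ANCOVA, the at-random code, LOCF and the per-protocol analysis are unaffected. It should still be corrected before database lock, because as written this check has almost no capacity to contradict a positive primary result.

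**What to change.** In SAP 6.5.7.3 and Protocol 10.4.3:

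1. Sort MDATA by `_IMPUTATION_`, add `NIMPUTE=1` to the second PROC MI statement, and add `BY _IMPUTATION_;`. This yields the 30 completed data sets the text promises.
2. State the missing steps: sum the five regional grades to tCFS, compute change from baseline, run the ANCOVA by `_IMPUTATION_`, and pool the 30 results with Rubin's rules.

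An equivalent route, valid only where the pattern is already monotone, is to run the second step directly on the original data with `NIMPUTE=30`. It would also help to say in one sentence how the not-at-random imputation is done for the Dryness Score.

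The cost is a few lines of code and a sentence or two of text in the SAP, with the same code correction in the protocol. No new data are needed and the primary analysis does not change. The confidence interval for this check becomes about 5.5 times wider than under the stacked reading (half-width about 0.41 instead of 0.07 in the 1,200-trial simulation), which is its correct width.

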6.5.7.4 Secondary Efficacy

6.5.7.4.1 Secondary Efficacy Analyses

The following secondary endpoints will be tested hierarchically:

1. CFB in Dryness Score (VAS scale) at Day 15
2. CFB in tCFS (NEI scale) at Day 15
3. CFB in VAS burning/stinging at Day 57
4. CFB in cCFS (NEI scale) at Day 57

Inference will only be made on these endpoints, at a 2-sided alpha = 0.05, if both primary endpoints and any higher order secondary endpoints are statistically significant at a 2-sided alpha = 0.05 in favor of NOV03.

Quantitative secondary efficacy endpoints will be summarized similarly to the primary efficacy endpoints.

The primary analysis of the secondary endpoints will use the FAS with available data per subject, assuming the overall study discontinuation rate is <5%. If the overall study discontinuation rate is $\geq 5\%$, then the primary analysis of the secondary endpoints will be based on imputation methodology as defined in Section 6.5.7.3 and the available data analyses will become robustness analyses.

6.5.7.4.2 Other Pre-specified Efficacy Analyses

The other pre-specified efficacy analyses will use the FAS with available data per subject:

[figure not shown]
1. CFB of Dryness Score (VAS) at Day 29
2. CFB in tCFS at Day 29
3. CFB in CFS central and inferior sub-regions (NEI scale) to each measured post-baseline visit
4. Proportion of tCFS responders (≥ 3 improvement based on NEI scale) at Day 57
5. Proportion of Dryness Score responders ($\geq 30\%$ improvement from baseline) at Day 57
6. CFB in VAS burning/stinging, sticky feeling, foreign body sensation, itching, blurred vision, sensitivity to light, pain, frequency of dryness, and awareness of dry eye symptoms at each measured post-baseline visit
7. CFB in OSDI at each measured post-baseline visit

Quantitative efficacy variables will be summarized descriptively (n, mean, standard deviation, median, min and max) by visit, and analyzed similarly to the primary endpoint at each measured visit. Least squares mean for each treatment group and for the difference between treatment groups will be presented from the model together with two-sided p-values and 95% confidence intervals. For assessments performed by eye, study eye and fellow eye will be summarized separately.

Endpoints evaluating the proportion of study eyes (or subjects) meeting pre-defined criteria will be presented and tested between treatment groups using logistic regression analysis adjusting for baseline tCFS score at each measured follow-up visit.

Sample SAS logistic regression code:

```
PROC LOGISTIC DATA=INDATA DESCENDING;
  CLASS <TREATMENT>;
  MODEL <ENDPOINT>=<TREATMENT> <BASELINE>;
RUN;
```

**6.5.7.6 Sensitivity Analyses****6.5.7.6.1 Sensitivity Analyses for Primary Efficacy Endpoints**

Two-sample t-tests (equal variance assumed), Wilcoxon rank sum tests and mixed-effect repeated measures analysis comparing treatment groups will be performed as sensitivity analyses. The mixed-effect repeated measures model will include treatment, baseline value, visit, and the interaction between treatment and visit as fixed effects, and subject as a random effect. An unstructured covariance matrix will initially be used to model the covariance among repeated measures; however, if the model fails to converge using this covariance structure, either heterogeneous TOEPLITZ, homogeneous TOEPLITZ, or compound symmetry will be implemented according to the Akaike information criterion with a correction for finite sample sizes (AICc).

Sample SAS two-sample t-test code:

```
PROC TTEST DATA=INDATA;
  CLASS <TREATMENT>;
  VAR <ENDPOINT>;
RUN;
```

Sample SAS Wilcoxon rank sum test code:

```
PROC NPAR1WAY DATA=INDATA WILCOXON;
  CLASS <TREATMENT>;
  VAR <ENDPOINT>;
RUN;
```

Sample SAS mixed-effect repeated measures analysis code:

```
PROC MIXED DATA=INDATA;
  CLASS <TREATMENT> <VISIT>;
  MODEL <ENDPOINT>=<TREATMENT> <VISIT> <TREATMENT>*<VISIT> <BASELINE>;
  REPEATED <VISIT> / SUBJECT=<SUBJECT> TYPE=UN;
  RANDOM <SUBJECT>;
```

```
ESTIMATE 'NOV03-SALINE' <TREATMENT> -1 1 / ALPHA=0.05 CL;  
RUN;
```

Where 'Saline' is <TREATMENT>=0 and 'NOV03' is <TREATMENT>=1.

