4.3 Visit Description

Subjects will be required to sign an Informed Consent before completing any trial related procedures. All trial procedures are listed in [Section 8.4](#) and in the schedule of assessments [Appendix 1](#). The ocular symptoms assessments and evaluations must be performed in the respective order as listed. IMP Dispensation is described in [Section 7.1.4](#).

Subjects will be instructed not to show or discuss the properties of the assigned IMP and/or their experience with the IMP with other trial participants, and not to show or discuss the IMP with the Investigator or site staff other than the dedicated dosing coordinator, unless instructed to do so.

Screening (Visit 0)

All assessments required for the screening visit must be done within 14 days before the randomization, baseline Visit 1. At least one eye must qualify with all of the following objective measures: Tear film break up time ≤ 5 sec, Schirmer's Test ≥ 5 mm, Meibomian gland dysfunction (MGD) defined as MGD score ≥ 3 , and total Corneal Fluorescein Staining (CFS) of $4 \leq x \leq 11$. Subjects who fail to qualify for the trial at screening may be rescreened as described in [Section 5.5](#).

Baseline Day 1 (Visit 1)

On Day 1 (Visit 1), eligible subjects will be evaluated for baseline signs and symptoms of dry eye disease and will be randomized to NOV03 QID or saline solution QID. Subjects will be given a 14-day supply and will self-administer a single drop of the first initial trial medication into each eye at the clinic. Subsequently the subject will be asked to complete an instillation comfort questionnaire. Each subject will be given a dosing diary to record

dosing. Study staff will help the subject to understand how to use the dosing diary and when the remaining doses should be taken.

Visits 2-4 / (ET)

Subjects will return to the clinic on Day 15±1 (Visit 2), 29±2 (Visit 3), and 57±2 (Visit 4/Early Termination (ET)) to be evaluated for signs and symptoms of dry eye disease. The subject will be asked to complete an eyedrop acceptability questionnaire during Visit 4. Collection and review of IMP will be performed (used and unused trial medication should be returned to the clinic) and new trial medication will be dispensed at Visit 2 and Visit 3. The dosing diary will be collected at the clinic during each visit and checked for compliance. Subjects will be discharged from the trial after all Visit 4/ET assessments have been completed.

Early Termination

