6.5.7.3 Primary Efficacy Analyses

The primary comparisons in this trial will be between NOV03 versus saline at Day 57 in the FAS with available data per subject using the following estimands

- Endpoint:
 - CFB in tCFS in the study eye at Day 57
 - CFB of Dryness Score (VAS) at Day 57
- Intercurrent event:
 - Discontinuation of study medications is ignored. [treatment policy strategy]
 - Non-optimal compliance is ignored. [treatment policy strategy]
 - Withdrawal due to any reason. Missing data not imputed. [hypothetical strategy if overall study discontinuation rate is <5%]
- Population-level summary:
 - Difference in the mean CFB in tCFS in the study eye at Day 57 between NOV03 and saline
 - Difference in the mean CFB of Dryness Score (VAS) at Day 57 between NOV03 and saline

If the overall study discontinuation rate in the FAS is $\geq 5\%$ then the primary analysis will be based on imputation methodology using the following estimands:

- Endpoint:
 - CFB in tCFS in the study eye at Day 57
 - CFB of Dryness Score (VAS scale) at Day 57
- Intercurrent event:
 - Discontinuation of study medications is ignored. [treatment policy strategy]
 - Non-optimal compliance is ignored. [treatment policy strategy]
 - Withdrawal due to lack of efficacy or adverse events: baseline observation carried forward (BOCF) is used to impute missing data [hypothetical strategy if overall study discontinuation rate $\geq 5\%$]
 - Missing data without withdrawal or withdrawal due to reasons other than lack of efficacy or adverse events: multiple imputations using randomized treatment-based Markov Chain Monte Carlo (MCMC) is used to impute missing data [hypothetical strategy if overall study discontinuation rate $\geq 5\%$]
- Population-level summary:
 - Difference in the mean CFB in tCFS in the study eye at Day 57 between NOV03 and saline
 - Difference in the mean CFB of Dryness Score (VAS scale) at Day 57 between NOV03 and saline

The primary comparison in this trial will be between NOV03 versus saline at Day 57. The primary efficacy endpoints (e.g. CFB in total corneal fluorescein staining [NEI scale] and Dryness Score) will be tested using hierarchical fixed sequence testing and summarized descriptively (n, mean, standard deviation, median, min, and max) and analyzed separately using an ANCOVA model with terms for baseline value, and treatment.

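### The repeated-measures sensitivity model uses one baseline slope for Days 15, 29 and 57, so its Day 57 difference can depart slightly from the available-data ANCOVA even with complete data; a baseline-by-visit term removes this

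*SAP*

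**What the plan says.** SAP 6.5.7.6.1 gives the fixed effects in words: "The mixed-effect repeated measures model will include treatment, baseline value, visit, and the interaction between treatment and visit as fixed effects". The sample code agrees: "MODEL <ENDPOINT>=<TREATMENT> <VISIT> <TREATMENT>*<VISIT> <BASELINE>". Both contain one baseline term and no product of baseline with visit. SAP 6.5.7.6.2 (secondary endpoints) and Protocol 10.4.5 repeat the same model. SAP 6.5.7.6.3 names the method for the other quantitative endpoints without writing a model out.

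On the covariance, 6.5.7.6.1 says: "An unstructured covariance matrix will initially be used to model the covariance among repeated measures". The contrast in the sample code is "ESTIMATE 'NOV03-SALINE' <TREATMENT> -1 1 / ALPHA=0.05 CL".

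The primary endpoints are instead "analyzed separately using an ANCOVA model with terms for baseline value, and treatment" (SAP 6.5.7.3), that is, a Day 57 regression with its own Day 57 baseline slope. On the role of the repeated-measures model, the SAP says only this: "Wilcoxon rank sum tests and mixed-effect repeated measures analysis comparing treatment groups will be performed as sensitivity analyses".

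**The concern.** The relation between baseline and change usually shifts over time: an early value tends to track baseline more closely than a late one. The plan lets the treatment effect vary by visit but holds this relation fixed. The fitted common slope is then a compromise between three visits, and it is applied at Day 57, where the ANCOVA uses the Day 57 slope.

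What is at stake is comparability, not validity. If the repeated-measures and ANCOVA results differ at Day 57, part of the gap may come only from the different baseline adjustment. A reader weighing the two side by side cannot tell that part from the effect of how missing values are handled. A little precision at Day 57 is also lost.

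**Working it through.** **1. Scale, from the plan's own figures.** SAP 6.5.10 assumes differences of -1.0 (SD 2.8) for tCFS and -10 (SD 28) for Dryness Score, 250 per arm, two-sided 0.05. The unadjusted standard error (SE) for tCFS is 2.8 × √(2/250) = 0.250, so power is Φ(1.0/0.250 − 1.96) = 97.9%. Dryness Score gives the same ratio, and 0.979² = 95.8%. The stated power reproduces.

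**2. Algebra.** Let dX be the between-arm difference in mean baseline and dY57 the between-arm difference in mean change at Day 57. With treatment, visit and their interaction in the model, and complete data:

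- repeated-measures estimate at Day 57 = dY57 − b_common × dX
- ANCOVA estimate = dY57 − b57 × dX
- departure = (b57 − b_common) × dX

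The departure is zero if the baseline means agree or if the fitted slopes agree. Since dX averages zero under randomisation, the departure averages about zero.

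**3. Size with complete data.** Assumptions not in the documents: baseline SD 2.0 (tCFS) or 20 (Dryness Score), between-visit residual correlation 0.6 falling with lag, and the slopes shown. SD(dX) = 2.0 × √(2/250) = 0.179 for tCFS and 1.789 for Dryness Score. The hand figure is |b57 − b_common| × SD(dX), using the assumed Day 57 slope and the mean fitted common slope. The other columns come from maximum-likelihood unstructured fits to 200 simulated trials per row.

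| Endpoint | Slopes, Days 15/29/57 | Mean b_common | Hand figure | Simulated SD of departure | ANCOVA SE | Ratio | Day 57 SE, one slope ÷ with interaction |
|---|---|---|---|---|---|---|---|
| tCFS | -0.4/-0.4/-0.4 | -0.404 | 0.001 | 0.006 | 0.239 | 0.03 | 1.000 |
| tCFS | -0.3/-0.4/-0.5 | -0.403 | 0.017 | 0.018 | 0.234 | 0.07 | 1.003 |
| tCFS | -0.2/-0.4/-0.6 | -0.423 | 0.032 | 0.032 | 0.226 | 0.14 | 1.009 |
| tCFS | -0.1/-0.4/-0.7 | -0.467 | 0.042 | 0.046 | 0.216 | 0.21 | 1.019 |
| Dryness | -0.3/-0.4/-0.5 | -0.409 | 0.163 | 0.164 | 2.34 | 0.07 | 1.003 |
| Dryness | -0.2/-0.4/-0.6 | -0.423 | 0.317 | 0.329 | 2.26 | 0.15 | 1.009 |

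The hand figure ignores sampling error in the slopes, which is why the first row is not zero in simulation. Significance at 0.05 differed from the ANCOVA in 0 or 1 of 200 trials per row.

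Other assumed inputs give the same order. With 280 per arm and baseline correlations falling over the three visits (0.6/0.5/0.4 or 0.6/0.45/0.3 for Dryness Score, 0.55/0.45/0.35 for tCFS), the SD was 0.10, 0.17 and 0.10 SE, and the Day 57 SE was 0.4 to 1.4% wider. A further set of assumed correlations gave 0.13 to 0.22 SE and 0.9 to 2.2%.

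**4. A given imbalance.** Take tCFS with slopes -0.2/-0.4/-0.6 and a baseline imbalance of two standard errors, dX = -2 × 0.179 = -0.358. The formula gives (-0.600 + 0.423) × (-0.358) = +0.063. Simulation moved the mean estimate from -1.008 (ANCOVA) to -0.947, a shift of 0.061. With dX = 0 the shift was zero.

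**5. With baseline by visit added.** Under complete data and unstructured covariance, the Day 57 contrast equalled the ANCOVA to rounding (largest gap 4e-14 for tCFS, 6e-13 for Dryness Score). These fits used the unstructured matrix alone, without the RANDOM statement that the sample code also prints.

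**6. With dropout.** For tCFS, 280 per arm and about 10% missing at random at Day 57 (assumed), the part of the gap to the available-data ANCOVA due to missing data had SD 0.041. The part due to the single slope had SD 0.020 (slopes -0.3/-0.4/-0.5) or 0.033 (slopes -0.2/-0.4/-0.6). The two are of similar order, and both are far below the SE of about 0.23.

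**7. The printed contrast.** The ESTIMATE statement carries no treatment-by-visit coefficients, so the procedure spreads it evenly over the three visits. With assumed effects of -0.6/-0.8/-1.0 it targets (-0.6 − 0.8 − 1.0)/3 = -0.8, not the Day 57 value of -1.0. Steps 2 to 6 concern a contrast that does target Day 57.

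**The case against.** A common baseline slope is a legitimate, fully pre-specified choice, identical in protocol and SAP, and it enters no decision rule. The model stands beside a t-test and a Wilcoxon test, neither of which adjusts for baseline at all, so departing from the ANCOVA with complete data is a feature of the whole set. All of this stands.

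A reader might infer that the model fails in a task of isolating the effect of missing data. The documents do not support that. They assign no such task; missing data are addressed by the LOCF and multiple-imputation robustness analyses (at random and not at random) in SAP 6.5.7.3 and 6.5.8.6.1. What remains is a limit on interpretation. The sample imputation code lists only baseline and the five regional scores, so a reader may still turn to the repeated-measures model as the analysis that brings Day 15 and Day 29 data to bear on Day 57.

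The benefit of the fix is also bounded. At 5% discontinuation or more, and the plan assumes 10%, the primary analysis becomes baseline carried forward for some withdrawals and MCMC imputation for the rest. A gap between that primary and the repeated-measures result mixes several missing-data assumptions whatever the baseline term. Clean attribution is available only against the available-data ANCOVA, which is then a robustness analysis.

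Finally, randomisation is stratified on baseline Dryness Score (<70 vs ≥70). Assuming normal baselines, near-perfect balance within strata and a cut between the mean and 1 SD from it, the SD of the imbalance falls to about 0.60 to 0.75 of its unstratified value. This takes 0.17 SE to about 0.10 to 0.13 SE. There is no stratification on tCFS, the first endpoint in the hierarchy.

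**Conclusion.** The point holds as a small specification improvement. The omitted interaction makes the Day 57 difference depart from the available-data ANCOVA by (b57 − b_common) × baseline imbalance. This requires both unequal slopes and a chance imbalance.

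The SD of the departure is roughly 0.1 to 0.2 SE when slopes differ, and about 0.03 SE when they do not. On Dryness Score, 0.17 SE is about 0.4 VAS points (0.17 × 2.3) against an assumed effect of 10, before any reduction from stratification. The Day 57 SE is wider by anything from under 0.5% to about 2%. These sizes rest on assumed baseline SDs, slopes and correlations; the algebra does not.

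It would be wrong to read this as a biased Day 57 estimate, since the departure averages zero, or as a threat to the primary test, alpha or power.

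**What to change.** Add `<BASELINE>*<VISIT>` to the MODEL statement in SAP 6.5.7.6.1. Add the interaction of baseline value with visit to the model wording in SAP 6.5.7.6.1, SAP 6.5.7.6.2 and Protocol 10.4.5, and state that the same model serves the quantitative endpoints in SAP 6.5.7.6.3.

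The ESTIMATE statement needs a separate correction so that the contrast targets Day 57; without it, the added term does not bring the printed result into line with the ANCOVA. With both changes, unstructured covariance and complete data, the two analyses agree, so any remaining gap to the available-data ANCOVA reflects missing-data handling.

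The cost is two extra parameters with about 500 subjects and one phrase per section. SAP Section 4 already provides for amendment before database lock and unmasking. The primary analysis, alpha and sample size do not change.
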